9.5. Treatment of Participants

This registry is an observational study to evaluate the effects of Oxbryta® (Voxelotol) in individuals with SCD. Participants will receive treatment with Oxbryta® (Voxelotol) as prescribed by their physician, as part of their usual care. Participants will be treated and evaluated per SOC and at the physician's discretion. There are no pre-defined treatment requirements.

9.5.1. Description of Oxbryta® (Voxelotol)

Oxbryta® (Voxelotol) is a hemoglobin S polymerization inhibitor indicated for the treatment of SCD in adults and pediatric patients 4 years of age and older.

Refer to the Oxbryta® (Voxelotol) US prescribing information (Oxbryta® (Voxelotol)® USPI)⁶ for details on the dosage, administration, formulation, packaging, storage, and handling of Oxbryta® (Voxelotol).

9.5.2. Concomitant Medications

A concomitant medication is defined as any prescription or over-the-counter preparation, including vitamins and supplements.

Pre-specified medications for SCD-related conditions taken by the participant from 12 months before screening through the end of study participation (5 years after the first dose of Oxbryta® (Voxelotol) treatment or early discontinuation) will be recorded in the CRF.

Treating physicians may prescribe the participant any additional medications or perform medical interventions they deem appropriate.

Refer to the Oxbryta® (Voxelotor)® USPI⁶ for details on concomitant medications and contraindications.

9.6. Data Sources

The main data source is through the electronic data capture in the study, while secondary data sources may include insurance claims, electronic medical records, hospital administrative data, and specific rare disease databases.

9.7. Study Data Collection

Data on participants will be collected at regular intervals and entered into the EDC system by study personnel at the study site beginning with their first dose of commercial Oxbryta® (Voxelotor). Data collection will include those data that are recorded in the participant's medical records/other secondary data sources and based on assessments performed as part of the participant's SOC. Study data that are not available in medical records or other secondary data sources will not be solicited from participants. The data to be collected in this study and target timepoints for data collection and entry are specified in the schedule of activities (SOA) in [Appendix 1](#).

There are not any required study procedures or assessments beyond the SOC. The SOA should be used as a guide for what data to enter and not for what assessments to perform. Therefore, if an assessment listed in the schedule of activity of the protocol is considered standard of care, the sites are asked to enter the assessment result into the study database. If an assessment is not conducted as SOC, the sites can just leave the relevant data fields blank.

Since Health-Related Quality of Life Measures (PROMIS, PGIC, NPRS and CGIC) are not commonly conducted as SOC, in order to allow important quality-of-life data to be gathered in the registry, questionnaires are provided to the sites and participants, and we recommend (but not require) the sites to perform these assessments.

9.8. Study Size

The sample size is selected to provide an estimation of the relationship between change in Hb and significant clinical events, for example VOCs and stroke that participants experience over the 5 years of the study. The total sample size of approximately 500 participants is expected to be enrolled.

9.9. Data Management

Study data will be collected at regular intervals and entered in case report forms (CRFs) via an electronic data capture (eEDC) system. All data management and data analysis will be performed by UBC using statistical software SAS®, SAS Institute Inc., Cary, NC, USA.

9.9.1. Case Report Forms (CRFs)/Data Collection Tools (DCTs)/Electronic Data Record

As used in this protocol, the term CRF should be understood to refer to either a paper form or an electronic data record or both, depending on the data collection method used in this study.

A CRF is required and should be completed for each included patient. The completed original CRFs are the sole property of Pfizer and should not be made available in any form to third parties, except for authorized representatives of Pfizer or appropriate regulatory authorities, without written permission from Pfizer. The investigator shall ensure that the CRFs are securely stored at the study site in encrypted electronic and/or paper *form and will be* [password protected or secured in a locked room] to prevent access by unauthorized third parties.

The investigator has ultimate responsibility for the collection and reporting of all clinical, safety, and laboratory data entered on the CRFs and any other data collection forms (source documents) and ensuring that they are accurate, authentic/original, attributable, complete, consistent, legible, timely (contemporaneous), enduring, and available when required. The CRFs must be signed by the investigator or by an authorized staff member to attest that the data contained on the CRFs are true. Any corrections to entries made in the CRFs or source documents must be dated, initialed, and explained (if necessary) and should not obscure the original entry.

The source documents are the hospital or the physician's chart. In these cases, data collected on the CRFs must match those charts.

9.9.2. Record Retention

To enable evaluations and/or inspections/audits from regulatory authorities or Pfizer, the investigator agrees to keep records, including the identity of all participating patients (sufficient information to link records, eg, CRFs and hospital records), all original signed informed consent/assent documents, copies of all CRFs/[DCTs], safety reporting forms, source documents, detailed records of treatment disposition, and adequate documentation of relevant correspondence (eg, letters, meeting minutes, and telephone call reports). The records should be retained by the investigator according to local regulations or as specified in the clinical study agreement (CSA), whichever is longer. The investigator must ensure that the records continue to be stored securely for so long as they are retained.

If the investigator becomes unable for any reason to continue to retain study records for the required period (eg, retirement, relocation), Pfizer should be prospectively notified. The study records must be transferred to a designee acceptable to Pfizer, such as another investigator, another institution, or to an independent third party arranged by Pfizer.

Study records must be kept for a minimum of 15 years after completion or discontinuation of the study, unless UBC and Pfizer have expressly agreed to a different period of retention via a separate written agreement. Record must be retained for longer than 15 years or as required by applicable local regulations.

The investigator must obtain Pfizer's written permission before disposing of any records, even if retention requirements have been met.

9.10. Data Analysis

There is not a separate statistical analysis plan (SAP) for this protocol. The detailed data analysis of endpoint measures are described in the [Section 9.11.3](#) and [Section 9.11.4](#).

9.11. Statistics

9.11.1. Analysis Population

Effectiveness and safety analyses will primarily be based on the treated population, defined as all participants receiving at least one dose of Oxbryta® (Voxelotor).

9.11.2. Sample Size

The sample size is selected to provide an estimation of the relationship between change in Hb and significant clinical events, for example VOCs and stroke that participants experience over the 5 years of the study. The total sample size of approximately 500 participants is expected to be enrolled.

9.11.3. Effectiveness Endpoint Measures Analyses

Baseline Demographic Characteristics:

Baseline demographic characteristics will be summarized descriptively.

Endpoints:

- Change from pre-Oxbryta® (Voxelotor) treatment period in Hb, hemolysis measures, measures of iron overload, and renal function over time will be summarized descriptively.
- Annualized rate of significant SCD-related clinical events, for example VOC, ACS, priapism, stroke, TIA, chronic or end stage kidney disease, iron overload, leg ulcers, cardiac malfunction, and PH will be calculated. The association between change in Hbhemolysis marker and rates of SCD-related clinical events will be evaluated.
- Rates of outpatient visits (including infusion center, acute care, or telemedicine visit), ED visits, hospitalizations, acute and chronic RBC transfusions, home oxygen supplementation, and renal dialysis will be summarized with a similar approach as incidences of SCD-related clinical events. The total cost associated with clinical interventions will be summarized descriptively.

- HRQoL measures over time will be summarized descriptively. Proportions of participants with improved HRQoL measures will be calculated and the associated 95% Clopper Pearson Exact confidence intervals will be constructed as appropriate.
- Rates of SCD-related clinical events, healthcare resource utilization, total cost associated with clinical interventions (if available) and HRQoL while on Oxbryta® (Voxelotor) treatment will be compared with the corresponding measures prior to the first dose of Oxbryta® (Voxelotor) treatment, as appropriate.

Subgroup analysis:

Similar comparisons may be performed between the subgroup of participants who discontinue Oxbryta® (Voxelotor) treatment but remain in the study and those participants who remain on Oxbryta® (Voxelotor).

Other subgroup or sensitivity analyses may be performed.

9.11.4. Safety Analysis

SAEs and protocol-specified AEs will be classified according to Medical Dictionary for Regulatory Activities (MedDRA). The frequency of AEs will be tabulated by system organ class, preferred term, severity, and relationship to Oxbryta® (Voxelotor) treatment.

9.12. Quality Control

9.12.1. Data Quality Assurance

- All participant data relating to the study will be recorded in the CRF unless transmitted to the Sponsor or designee electronically (eg, laboratory data). The study doctor is responsible for verifying that data entries are accurate and correct by physically or electronically signing the CRF.
- Guidance on completion of CRFs will be provided in the CRF completion guideline.
- The study doctor must permit as needed study-related monitoring, audits, IRB review, and regulatory agency inspections and provide direct access to source data documents.
- Monitoring details will be provided in the monitoring plan.
- Records and documents, including signed ICFs, pertaining to the conduct of this study must be retained by the study doctor for 2 years after study completion unless local regulations or institutional policies require a longer retention period. No records may be destroyed during the retention period without the written approval of the Sponsor. No records may be transferred to another location or party without written notification to the Sponsor.

9.12.2. Source Documents

- Source documents provide evidence for the existence of the participant and substantiate the integrity of the data collected. Source documents are filed at the study site.
- For this study, source data includes data recorded in the participant's medical records and other secondary data sources and collected as part of the participant's usual medical care.
- The study doctor must maintain accurate documentation (source data) that supports the information entered in the CRF.
- Study monitors will confirm that data entered into the CRF by authorized site personnel are accurate, complete, and verifiable from source documents.

9.12.3. Essential Documentation Requirements

The Sponsor or Sponsor's representative will collect from the study site the required essential regulatory documents per ICH guidance prior to enrollment of any participant in the study.

9.13. Strengths and Limitations of the Research Methods

A post marketing product registry enables robust and systematic data collection on product use in the real-world setting. It can also provide details on measures such as care pattern, long-term efficacy and safety which require long-term follow up and large number of patients.

Due to the observational study design, limitations include reliance on data included in participants' medical records, limited monitoring and quality control for data collection, patient population and standard of care vary among study sites, and susceptibility to multiple sources of bias for comparing outcomes.

9.14. Other Aspects

9.14.1. Financial Disclosure

Financial Disclosure statements will be handled in a separate agreement apart from the protocol, kept on file and submitted, as applicable, with any subsequent license application.

9.14.2. Study and Site Start and Closure

9.14.2.1. First Act of Recruitment

The study start date is the date on which the study is open for recruitment of participants.

The first act of recruitment is the first site open and will be the study start date.

9.14.2.2. Site Closure

Study sites will be closed upon study completion. A study site is considered closed when the Sponsor/CRO has confirmed that all participant data entered into EDC is confirmed final and signed by the Principal Investigator (PI); all required documents and study supplies have been destroyed and a study-site closure visit has been performed.

The Sponsor reserves the right to close the study site at any time for any reason at the sole discretion of the Sponsor. The study doctor may also initiate study-site closure at any time, provided there is reasonable cause and sufficient notice is given in advance of the intended termination.

Reasons for the early closure of a study site by the Sponsor or study doctor may include but are not limited to:

- Failure of the study doctor to comply with the protocol, the requirements of the IRB or local health authorities, the Sponsor's procedures, or GCP guidelines
- Inadequate or no recruitment (evaluated after a reasonable amount of time) of participants by the study doctor
- Enrollment goal met earlier than expected

The study doctor shall inform the participant and the Institutional Review Boards (IRBs), of any site closure.

9.14.2.3. Study Termination

The Sponsor reserves the right to terminate the study or close the study site at any time for any reason at the sole discretion of the Sponsor.

Reasons for terminating the study may include, but are not limited to the following:

- Discontinuation of further Oxbryta® (Voxelotor) development

In any instance of early termination of the study, the Sponsor will notify, in writing, the study doctors, and the IRBs, and will specify the reason(s) for termination.

The study doctor shall inform the participant and of any early termination of the study.

10. PROTECTION OF HUMAN PARTICIPANTS

10.1. Patient Information

All parties will comply with all applicable laws, including laws regarding the implementation of organizational and technical measures to ensure protection of patient personal data. Such measures will include omitting patient names or other directly identifiable data in any reports, publications, or other disclosures, except where required by applicable laws.

The personal data will be stored at the study site in encrypted electronic and/or paper form and will be password protected or secured in a locked room to ensure that only authorized study staff have access. The study site will implement appropriate technical and organizational measures to ensure that the personal data can be recovered in the event of disaster. In the event of a potential personal data breach, the study site shall be responsible for determining whether a personal data breach has in fact occurred and, if so, providing breach notifications as required by law.

To protect the rights and freedoms of natural persons with regard to the processing of personal data, when study data are compiled for transfer to Pfizer and other authorized parties, patient names will be removed and will be replaced by a single, specific, numerical code, based on a numbering system defined by Pfizer. All other identifiable data transferred to Pfizer or other authorized parties will be identified by this single, patient-specific code. The investigator site will maintain a confidential list of patients who participated in the study, linking each patient's numerical code to his or her actual identity. In case of data transfer, Pfizer will maintain high standards of confidentiality and protection of patients' personal data consistent with the clinical study agreement and applicable privacy laws.

To protect the rights and freedoms of natural persons with regard to the processing of personal data, when study data are compiled for transfer to Pfizer and other authorized parties, any patient names will be removed and will be replaced by a single, specific, numerical code. All other identifiable data transferred to Pfizer or other authorized parties will be identified by this single, patient-specific code. In case of data transfer, Pfizer will maintain high standards of confidentiality and protection of patients' personal data consistent with the CRO SOP and applicable privacy laws.

10.2. Patient Consent

A signed and dated consent and/or assent form (age <18 years) will be obtained before any data collection for the study.

For pediatric participants, consent should be obtained from at least one parent (or both if it is required per study site policy) or the participant's legally authorized representative.

As applicable, the consent will include language for the use of de-identification and tokenization technology that will allow for the acquisition and linkage of the participant to their healthcare data that exists in pharmacy and medical administrative claims databases.

Guidelines for the informed consent/assent process are outlined in [Section 10.7.2](#).

PFIZER CONFIDENTIAL

CT24-WI-GL02-RF02 5.0 Non-Interventional Study Protocol Template For Secondary Data Collection Study

01-Aug-2023

Page 36 of 64

10.3. Patient Withdrawal

10.3.1. Participant ID Number

Upon execution of consent/assent, all participants will be given a unique participant ID number. This number will be used to identify the participant throughout the study and must be used on all study documentation related to that participant.

10.3.2. Eligibility Assessment

Confirmation of eligibility (all inclusion/exclusion criteria) will be performed at pre-Oxbryta® (Voxelotor) treatment period.

10.3.3. Medical History, Demographic Data, and Insurance Information

Medical history will be recorded for up to 12 months prior to the first dose of Oxbryta® (Voxelotor) (retrospective data). Medical history will include all available SCD genotype results and significant medical history, including hematological parameters.

Demographics (sex, race, ethnicity, and age) and SCD characteristics will be recorded at pre-Oxbryta® (Voxelotor) treatment period, using the most recent data before enrollment.

Information on the participant's insurance payer will also be collected (eg, Medicaid, Medicare, dual eligible, private, or self-insured).

10.3.4. SCD Genotype

SCD genotype (at pre-Oxbryta® (Voxelotor) treatment period) only for medical diagnosis of SCD, if a diagnosis is not documented in the medical chart.

10.3.5. Physical Examination

Height and weight will be collected at the screening visit for all participants of age 18 and above, and at screening and all follow up visits for participants up to age 18. Pulse oximetry [%SpO₂] will be collected for all participants at screening and all follow up visits per SOC.

10.3.6. Effectiveness Data

10.3.6.1. Clinical Outcomes

10.3.6.1.1. Laboratory Assessments

The following data will be recorded on the CRF:

For pre-Oxbryta® (Voxelotor) Treatment Visits, only the most recent results from regularly scheduled outpatient visit will be entered.

For post-Oxbryta® (Voxelotor) Treatment Regularly Scheduled Outpatient Visits, all available results during the data collection period will be entered.

For post-Oxbryta® (Voxelotor) Acute Visits (Emergency Department, Hospitalization, Acute Pain/Infusion Center), only the results on the day of presentation (or first available results during the visit) and day of discharge will be entered, if available.

The following data from the most recent results will be recorded in the CRF:

- Hb (including % HbF at baseline and all follow up visits), white blood cells (WBC), absolute neutrophil count (ANC), mean corpuscular volume (MCV), mean corpuscular hemoglobin concentration (MCHC), Platelets, aspartate aminotransferase (AST), alanine aminotransferase (ALT), and lactate dehydrogenase (LDH).
- Hemolysis measures, including % reticulocytes, absolute reticulocytes, bilirubin (total, direct, and indirect)
- Measures of iron overload (ferritin, iron, TIBC, T2*MRI)
- Creatinine (Serum)
- Albuminuria (urine albumin/creatinine ratio [ACR])
- Hemoglobinuria (urine dipstick positive for blood +1 or greater and ≤ 2 RBC by high power field)
- Serum cystatin C
- eGFR calculated using CKD-EPI equation

10.3.6.1.2. SCD Complications

For the pre Oxbryta® (Voxelotor) treatment SCD complications, all events that occurred within 12 months prior to starting Oxbryta® (Voxelotor) treatment will be recorded in the CRF.

For the post- Oxbryta® (Voxelotor) treatment SCD complications, all events occurring since the last collection timepoint will be recorded in the CRF.

10.3.6.1.3. Vaso-Occlusive Crises (VOCs) and Acute Chest Syndrome (ACS)

VOC data as documented in the participant's medical record will be collected and will include data on VOC events, duration, intensity, and associated interventions.

A VOC is defined as an acute episode of pain that:

- Has no medically determined cause other than a vaso-occlusive event, and
- Results in a visit to a medical facility (hospitalization, emergency department, urgent care center, outpatient clinic, or infusion center), or results in a remote contact with a healthcare provider; and
- Requires parenteral narcotic agents, parenteral nonsteroidal anti-inflammatory drugs (NSAIDs), or an increase in treatment with oral narcotics.

Data related to any events of ACS will be collected.

The events may have occurred in a medical setting (hospital, clinic, emergency room) or at home.

10.3.6.1.4. Priapism

Occurrence of priapism events will be collected. All data from events occurring during the period since the last collection timepoint will be recorded in the CRF.

10.3.6.1.5. Stroke and Transient Ischemic Attack

Data related to any events of stroke (Ischemic, Hemorrhagic, and Silent), and Transient ischemic attack (TIA), for example, as identified via MRI or TCD (TAMMV measures in ICA, MCA, ACA), will be collected.

10.3.6.1.6. Leg Ulcers

Data on leg ulcer(s) assessments will be collected, including information on existing and new ulcers.

10.3.6.1.7. Cardiac Malfunction and Pulmonary Hypertension

Cardiac malfunction, for example, as assessed by cardiac ECHO or cardiac catheterization will be collected.

Clinical indicators of PH (such as the 6-minute walk test, dyspnea on exertion, hepatic congestion, etc.) will also be collected.

10.3.6.1.8. Other SCD Complication

Data on other SCD complications will be collected. This may include sickle cell anemia, splenomegaly/splenectomy, dactylitis, cholelithiasis/cholecystectomy, aplastic crisis, chronic or end stage kidney disease (as defined by GFR <60), iron overload (as diagnosed by T2* MRI or R2* MRI), pneumonia, retinopathy, avascular necrosis, deep vein thrombosis, and chronic/acute pain.

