Regardless of how long participants have been on Oxbryta® (Voxelotor) when they enroll in the study, participants will be followed for up to 5 years after their first dose of Oxbryta® (Voxelotor) treatment, or until they withdraw their consent to participate, or are discontinued from the study. Treatment, including interruptions and restarting treatment, will continue at the discretion of the treating physician, and there are no pre-defined treatment requirements. Participants may receive any additional medications prescribed by their treating physician or have any medical interventions that are deemed appropriate by the treating physician or study doctor. The participant or treating physician may discontinue Oxbryta® (Voxelotor) at any time. Participants who discontinue treatment with Oxbryta® (Voxelotor) earlier than 5 years will continue to be followed on study to collect clinical and health-related quality of life (HRQoL) outcomes for up to 5 years after their first dose of Oxbryta® (Voxelotor) treatment.

Participant safety and tolerability will be assessed throughout the study data collection period by the study doctor and reported to the Sponsor.

The overall study design is illustrated in [Figure 1](#).

Figure 1: Study Schema

SOC, standard of care.

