Appendix 1. Schedule of Activities

| Data Collection/Procedure | Pre-Oxbryta® (Voxelotol) treatment period | Study Data Collection Period | | | | | | | | | | | |
|---|---|------------------------------|---|---|----|----|----|----|----|----|----|----|----|
| | | 3 | 6 | 9 | 12 | 18 | 24 | 30 | 36 | 42 | 48 | 54 | 60 |
| Month Intervals | -12 to 1 | | | | | | | | | | | | |
| Informed Consent/Accent ^a | X | | | | | | | | | | | | |
| Review of eligibility ^b | X | | | | | | | | | | | | |
| Medical history and SCD genotype ^c | X | | | | | | | | | | | | |
| Physical examination (including height and weight) and vital signs ^d | X | X | X | X | X | X | X | X | X | X | X | X | X |
| Clinical outcomes and interventions ^e | X | X | X | X | X | X | X | X | X | X | X | X | X |
| Health resource utilization ^f | X | X | X | X | X | X | X | X | X | X | X | X | X |
| HRQoL assessments (PROMIS, NPRS, and exercise tolerance) ^g | X | X | X | X | X | X | X | X | X | X | X | X | X |
| CGIC and PGIC | | X | X | X | X | X | X | X | X | X | X | X | X |
| SCD medications ^h | X | X | X | X | X | X | X | X | X | X | X | X | X |
| Safety data ⁱ | X | X | X | X | X | X | X | X | X | X | X | X | X |
| Serum pregnancy test ^j | X | | | | | | | | | | | | |
| Urine pregnancy test ^k | | X | X | X | X | X | X | X | X | X | X | X | X |

CGIC=Clinical Global Impression of Change; HRQoL=Health-related quality of life; PGIC=Patient Global Impression of Change; PROMIS=Patient-Reported Outcomes Measurement Information System; NPRS=Numerical Pain Rating Scale.

NOTE: With the exception of informed consent/assent, all other data listed above are required to be collected if assessments are performed as part of the participant's standard-of-care; the data from these assessments will be collected at the timepoints indicated (if available) and will include all data available for the period between the timepoints.

- A signed and dated consent and/or assent form (age <18 years) will be obtained before any data collection for the study. For pediatric participants, consent should be obtained from at least one parent (or both if it is required per investigational site policy) or the participant's legally authorized representative.
- Inclusion and exclusion criteria should be reviewed at the pre-Oxbryta® (Voxelotol) treatment period to ensure participant eligibility is met.

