- Change from pre-Oxbryta treatment period in the following Chemistry parameters corresponding to treatment with Oxbryta® (Voxelotol):
 - Ferritin

Analysis: Observed and change from pre-Oxbryta treatment period on ferritin will be summarized descriptively ([Section 4.7](#)) by visit.

- Change from pre-Oxbryta® (Voxelotol) treatment period in renal function:
 - Creatinine (Serum)
 - Albuminuria (urine albumin/creatinine ratio [ACR])
 - Hemoglobinuria (urine dipstick positive for blood +1 or greater and ≤ 2 RBC by high power field)
 - Serum cystatin C
 - Estimated eGFR calculated using the CKD-EPI equation

Analysis: Observed and change from pre-Oxbryta treatment period on Creatinine (Serum), Albuminuria, Hemoglobinuria, Serum cystatin C and eGFR will be summarized descriptively ([Section 4.7](#)) by visit

- Rate of SCD complications including acute pain crisis, acute chest syndrome

(ACS), priapism, stroke, and transient ischemic attack (TIA), chronic or end stage kidney disease, iron overload, leg ulcers, cardiac malfunction, and pulmonary hypertension (PH) and RBC transfusions.

Analysis:

The number and percentage of participants with SCD complications including acute pain crisis, ACS, priapism, stroke, chronic or end stage kidney disease iron overload, leg ulcers, cardiac malfunction and PH and RBC transfusions will be summarized by SOC and PT throughout the treatment period.

The annualized incidence rate of SCD complications including acute pain crisis, ACS, priapism, stroke, chronic or end stage kidney disease iron overload, leg ulcers, cardiac malfunction and PH and RBC transfusions will be summarized by SOC and PT throughout the treatment period.

- **PGIC**

PGIC includes 7 response categories: Very much improved, much improved, minimally improved, no change, minimally worse, much worse and very much worse.

Analysis: The PGIC will be summarized as numbers and percentages by visit for each response category.

- **CGIC**

CGIC includes 7 response categories: Very much improved, much improved, minimally improved, no change, minimally worse, much worse and very much worse.

Analysis: The CGIC will be summarized as numbers and percentages by visit for each response category.

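### Chronic or end stage kidney disease is defined only by a GFR below 60, with no persistence rule, so a site may report one transient low value as chronic disease

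*Protocol*

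**What the plan says.** Protocol 10.3.6.1.8, among the other SCD complications to be collected, includes "chronic or end stage kidney disease (as defined by GFR <60". Neither document adds a duration, a confirmatory value, units, a limit by visit type or a separate end stage threshold.

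SAP 4.7.3 carries the event into the analysis undefined, within a list that includes "chronic or end stage kidney disease, iron overload, leg ulcers, cardiac malfunction, and pulmonary hypertension (PH) and RBC transfusions". It plans the number and percentage of participants and the annualized incidence rate over the treatment period. SAP 4.7 defines that rate as total events over total patient-years and gives no once-per-participant rule for a lasting condition.

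SAP 4.7.4 says how an event gets in: the site answers yes to the question on the SCD complications/AE form that asks whether this is an SCD complication. Neither document derives kidney disease from the entered GFR values.

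Protocol 10.3.6.1.1 governs laboratory entry:
- before first dose, "only the most recent results from regularly scheduled outpatient visit will be entered";
- after first dose, for scheduled outpatient visits, "all available results during the data collection period will be entered";
- after first dose, for acute visits, "only the results on the day of presentation (or first available results during the visit) and day of discharge will be entered", if available.

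Pre-dose complications follow a different rule, in Protocol 10.3.6.1.2: "all events that occurred within 12 months prior to starting Oxbryta® (Voxelotor) treatment will be recorded in the CRF".

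**The concern.** Chronic disease is lasting by meaning, but the criterion can be met by one value on one day. Take a hypothetical participant admitted in crisis with a GFR of 50 at presentation and 95 at discharge. Both values go into the CRF, the first meets the stated definition, and nothing tells the site that it should not count. Sites that apply the wording literally and sites that use clinical judgement would report differently, across the 35 or 45 sites that the protocol gives in its abstract and in 9.1.1.1. The same cut also pools moderate loss of function with end stage disease.

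End-organ damage is part of the primary objective, and SAP 4.7.3 keeps SCD-related clinical events within the abbreviated report. A false chronic kidney disease event would therefore appear in both the count and the rate of a registry that Protocol 7 designates a PASS.

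**Working it through.** The plan states no expected rate or error rate for this event, so there is no figure to reproduce. The calculation below shows how much a persistence rule could matter if every value below 60 were reported. That automatic trigger is an assumption and is not what the plan describes.

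**Inputs from the documents**
- Threshold: GFR below 60 (Protocol 10.3.6.1.8).
- Follow-up: "participants will be followed for up to 5 years after their first dose" (Protocol 9.1.1.1).
- Post-dose collection timepoints: months 3, 6, 9, 12, 18, 24, 30, 36, 42, 48, 54 and 60, which is 12 (Protocol Appendix 1). Data entry "will include all data available for the period between the timepoints", so a participant may have more than 12 results. Those who leave early, or who were already on drug at enrollment, may have fewer prospective ones.

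**Inputs assumed**
- Stable true GFR μ, from 70 to 90.
- Independent normal readings with within-person CV of 10%, varied to 8% and 5%.
- One reading per timepoint, k = 12.

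**Formulas**
- One reading below 60: p = Φ((60 − μ)/(CV × μ)).
- At least one of 12: 1 − (1 − p)^12.
- Two consecutive of 12: start with a = 1 and b = 0; at each reading set a to (a + b)(1 − p) and b to (old a) × p; after 12 readings the probability is 1 − a − b.
- Any two of 12: 1 − (1 − p)^12 − 12p(1 − p)^11.

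Example, μ = 75 and CV 10%: (60 − 75)/7.5 = −2.0, so p = 0.0228, and 1 − 0.9772^12 = 0.24.

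**Results, CV 10%**

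| True GFR | One reading | At least one of 12 | Two consecutive of 12 | Any two of 12 |
|---|---|---|---|---|
| 70 | 7.7% | 62% | 5.9% | 23% |
| 75 | 2.3% | 24% | 0.6% | 2.9% |
| 80 | 0.6% | 7.2% | 0.04% | 0.2% |
| 85 | 0.2% | 1.9% | <0.01% | 0.02% |
| 90 | 0.04% | 0.5% | <0.01% | <0.01% |

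**Sensitivity**
- CV 8%: at least one of 12 is 36% at GFR 70, 7.2% at 75 and 1.1% at 80.
- CV 5%: it is 2.5% at GFR 70 and 0.04% at 75.
- Assuming p directly, without a GFR model, from 0.5% to 5% per result: at least one of 12 runs from 5.8% to 46%, and two consecutive from 0.03% to 2.6%.
- Positive correlation between readings would make the rise with k smaller but would not remove it.

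Two points follow. The effect is concentrated in participants whose true GFR lies near the cut. And a rule of any two low values is much weaker than two consecutive ones: at GFR 70 it still labels 23% of stable participants, against 5.9%.

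**The case against.** The strongest objection is that laboratory values do not become events by themselves. A site has to report the complication, and many clinicians would not report a resolved acute dip as chronic kidney disease. That stands, and it is why the table is an illustration and not an estimate of misclassification. It does not remove the problem: the only criterion the protocol gives sites is the one that a transient value meets, so any filtering is unguided.

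A reader might also infer a pre/post bias, since one laboratory set is entered before first dose and many after it, including acute-visit values. The documents do not support that step. Pre-dose complications are collected as events over 12 months, not read from one laboratory set. The SAP's explicit pre/post rates cover acute pain crisis/VOC only. The protocol's wider comparison in 9.11.3 is made only as appropriate. Setting a chance accumulated over 12 readings against a single reading also ignores that the SAP divides by patient-years.

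The magnitude depends on inputs that the documents do not give. Neither a GFR distribution nor a within-person CV is stated, and at a true GFR of 90 the effect is negligible. This stands, so no cohort-level figure can be given.

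Finally, SAP 4.7.3 summarizes creatinine, cystatin C and eGFR by visit, so lasting loss of function can be seen elsewhere in the report. That helps interpretation but does not correct the event count.

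**Conclusion.** The point holds as a defect of definition. The stated rule lets one transient value, including one taken during an acute visit, be reported as chronic or end stage kidney disease, and the SAP would count it in the percentage and the annualized rate. This follows from the text alone.

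The size of any inflation is unknown because reporting depends on the site. Under an automatic trigger, 12 independent readings and CV 10%, the chance of at least one low value without any true change runs from about 0.5% at GFR 90 to 62% at GFR 70; a smaller CV lowers it. These are cumulative chances per participant, not rates per year. No pre/post bias for this event is shown. The change should be made, since it corrects a wrong rule and uses data already collected.

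**What to change.** In Protocol 10.3.6.1.8 and SAP 4.7.3:
- Count chronic kidney disease only when two consecutive scheduled-outpatient GFR results at least 90 days apart are below 60, or when a clinician's diagnosis is documented. If scheduled results fall closer together, all of them across the 90 days should be below 60. Date the laboratory-confirmed event at the first low result, and count the event once per participant.
- Report end stage kidney disease separately, from a documented diagnosis or from the renal dialysis data collected under Protocol 10.3.6.2.
- List isolated or acute-visit values below 60 as laboratory findings, not as this complication.
- For events that sites have already reported, apply the confirmation as an SAP derivation on the entered GFR results. New CRF guidance alone would not reclassify them.

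The 90-day interval is a proposal; the documents give no figure. It fits the Appendix 1 schedule, where timepoints are three months apart in year 1 and six months apart after that.

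The cost is definition wording and one derivation. Healthcare resource utilization is not in the SAP 4.3 variable list, so the dialysis data would have to be brought into the analysis. The downside is fewer events, and a value first low at the last visit cannot be confirmed.
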